### **23.3 Serious Adverse Event Reporting**

All SAEs, other reportable information, and follow-up information must be reported within 24 hours of learning of the event by completing the SAE form within the eCRF. As a back-up, the site may fax a completed serious adverse event form to the fax number indicated in the Emergency Contacts section and confirming by phone or e-mail that the fax was received. Plexxikon (or designee) will process and evaluate all SAEs as soon as the reports are received. For each SAE received, Plexxikon will make a determination as to whether the criteria for expedited reporting have been met.

Plexxikon (or designee) is responsible for reporting relevant SAEs to the relevant regulatory authorities and participating investigators, in accordance with FDA regulations 21 CFR 312.32, ICH guidelines, European Clinical Trials Directive (Directive 2001/20/EC), and/or local regulatory requirements.

Reporting of SAEs by the investigator to the Institutional Review Board (IRB) or Ethics Committee (EC) will be done in accordance with the standard operation procedures and policies of the IRB/EC. Adequate documentation must be maintained showing that the IRB/EC was properly notified.

#### **24.0 STUDY SUSPENSION, TERMINATION, AND COMPLETION**

The Sponsor may suspend or terminate the study or any part of the study at any time for any reason. If the investigator suspends or terminates the study, the investigator will promptly inform the Sponsor and the IRB/IEC and provide them with a detailed written explanation. The investigator will also return all study drug, containers, and other study materials to the contract distribution center, or destroy the materials at the investigative site. Upon study completion, the investigator will provide the Sponsor, IRB/IEC, and regulatory agency with final reports and summaries as required by regulations. For IND studies, the investigator must submit a written report to the Sponsor and the IRB/IEC within 3 months after the completion or termination of the study.

#### **25.0 INFORMED CONSENT**

The investigator will provide for the protection of the patients by following all applicable regulations. These regulations are available upon request from the Sponsor. The informed consent form used during the informed consent process must be reviewed by the Sponsor and approved by the IRB/IEC.

Before any procedures specified in the protocol are performed, a patient must:

- Be informed of all pertinent aspects of the study and all elements of informed consent.
- Be given time to ask questions and time to consider the decision to participate.
- Voluntarily agree to participate in the study.
- Sign and date an IRB/IEC approved informed consent form.

#### **26.0 PROTOCOL AMENDMENTS**

Any significant change in the study requires a protocol amendment. An investigator must not make any changes to the study without IRB/IEC and Sponsor approval except when necessary to eliminate apparent immediate hazards to the patients. A protocol change intended to eliminate an apparent immediate hazard to patients may be implemented immediately, but the change must then be documented in an amendment, reported to the IRB/IEC within 5 working days, and

submitted to the appropriate regulatory agency in the required time frame. All protocol amendments must be reviewed and approved following the same process as the original protocol.

## **27.0 QUALITY CONTROL AND ASSURANCE**

The Sponsor performs quality control and assurance checks on all clinical studies that it sponsors. Before enrolling any patients in this study, Sponsor personnel and the investigator review the protocol, the investigator's brochure, the eCRFs and instructions for their completion, the procedure for obtaining informed consent, and the procedure for reporting AEs and SAEs. A qualified representative of the Sponsor will monitor the conduct of the study. During these site visits, information recorded in the eCRFs is verified against source documents.

## **28.0 DIRECT ACCESS, DATA HANDLING, AND RECORD KEEPING**

### **28.1 Investigator**

The investigator will permit study-related monitoring, audits, IRB/IEC review, and regulatory inspections by providing direct access to source data and documents.

All study-related information will be recorded on source documents. All required data will be recorded in the eCRFs. All eCRF data must be submitted to the Sponsor throughout and at the end of the study.

If an investigator retires, relocates, or otherwise withdraws from conducting the study, the investigator must notify the Sponsor to agree upon an acceptable storage solution. Regulatory agencies will be notified with the appropriate documentation.

All laboratory and clinical data gathered in this protocol will be stored in a password-protected database. All patient information will be handled using anonymous identifiers. Linkage to patient study data is only possible after accessing a password-protected database. Access to the database is only available to individuals directly involved in the study.

Patient personal health information that is accessed for this study will not be reused or disclosed to any other person or entity, or for other research.

### **28.2 Sponsor**

The data will be checked for completeness and correctness by real-time online checks as it is entered into the electronic data capture system [Tempo] used to collect the data. Off-line checks will also be run to perform any additional data review required. Discrepancy reports will be generated accordingly and transferred to the study center for resolution by the investigator or designee.

## 29.0 PRE-STUDY DOCUMENTATION

The investigator must provide the Sponsor with the following documents BEFORE enrolling any patients:

- Completed and signed form 1572.
- All applicable country-specific regulatory forms.
- Current signed and dated curricula vitae for the investigator, subinvestigators, and other individuals having significant investigator responsibility who are listed on the Form 1572 or equivalent, or the clinical study information form.
- Copy of the IRB/IEC approval letter for the protocol and informed consent. All advertising, recruitment, and other written information provided to the patient must be approved by the IRB/IEC. Written assurance of continuing approval (at least annually) as well as a copy of the annual progress report submitted to the IRB/IEC must also be provided to the Sponsor.
- Copy of the IRB/IEC-approved informed consent document to be used.
- Where applicable, a list of the IRB/IEC members or a FWA/DHHS number.
- Copy of the protocol sign-off page signed by the investigator.
- Copy of the current medical license of the principal Investigator and any subinvestigators.
- Fully executed Clinical Trial Agreement.
- Where applicable, a financial disclosure form for the investigator, subinvestigators, and other individuals who have significant investigator responsibility and are listed on the Form 1572.
- A written document containing the name, location, certification number, and date of certification of the laboratory to be used for laboratory assays and those of other facilities conducting tests. This document should be returned along with the lab director's curriculum vitae and active medical license. The Sponsor must be notified if the laboratory is changed or if any additional laboratory is to be used.
- List of normal laboratory values and units of measure for all laboratory tests required by the protocol. This is required for each laboratory to be used during the study. The Sponsor must be notified if normal values or units of measurement change.

## 30.0 RECORDS RETENTION

The investigator shall retain and preserve 1 copy of all data generated in the course of the study, specifically including but not limited to those defined by GCP as essential, for the longer of: (i) 2 years after the last marketing authorization for the study drug has been approved or the Sponsor has discontinued its research with respect to such drug or (ii) such longer period as required by applicable global regulatory requirements. At the end of such period, the investigator shall notify the Sponsor in writing of its intent to destroy all such material. The Sponsor shall

have 30 days to respond to the investigator's notice, and the Sponsor shall have a further opportunity to retain such materials at the Sponsor's expense.

**ATTACHMENT 1: LABORATORY TESTS****Hematology**

Hemoglobin and hematocrit  
 White blood cell count with differential  
 Platelet count

**Serum Chemistry**

Sodium	Uric acid
Potassium	Total protein
Chloride	Albumin
CO 2	Total and direct bilirubin
Calcium	Aspartate aminotransferase (AST)
Phosphorus	Alanine aminotransferase (ALT)
Glucose	Alkaline phosphatase (AP)
Blood urea nitrogen	Lactate dehydrogenase (LDH)
Creatinine	

**Serum pregnancy test (β-HCG):** women of child-bearing potential

**Blood Response Biomarkers:**

- CSF-1
- Biomarkers of kinase inhibition and myeloid cell recruitment
- CD14/CD16 mononuclear cells

**Tissue Response Biomarkers in Formalin-Fixed Surgical Tissue**

- MGMT methylation
- CSF1R and CSF1
- Tumor-associated macrophages
- Other prognostic markers as appropriate

Because the identification of new response prediction or early response biomarkers of disease activity is a rapidly developing field, the definitive list of analyses remains to be determined, and may include additional markers of macrophage activity, in addition to anti-tumor biomarkers that may be related to PLX3397 treatment.

**ATTACHMENT 2: STRONG CYP3A4 INHIBITORS AND INDUCERS**

Strong Inhibitors	Strong Inducers
Protease inhibitors	Anticonvulsants, mood stabilizers

 
• Ritonavir
 
• Indinavir
 
• Nelfinavir
 
	
 
• Phenytoin
 
• Carbamazepine
 
• Oxcarbazepine
 

Macrolide antibiotics	Non-nucleoside reverse transcriptase inhibitors

 
• Erythromycin
 
• Telithromycin
 
• Clarithromycin
 
	
 
• Efavirenz
 
• Nevirapine
 
• Etravirine
 

Azole antifungals	Phenobarbital (barbiturate)

 
• Fluconazole
 
• Ketoconazole
 
• Itraconazole
 
	Rifampicin (bactericidal)
Chloramphenicol (antibiotic)	Modafinil (stimulant)
Nefazodone (antidepressant)	Hyperforin (constituent of St Johns Wort)
Bergamottin (constituent of grapefruit juice)	Cyproterone (antiandrogen, progestin)
Aprepitant (antiemetic)	
Verapamil (calcium channel blocker)	

**ATTACHMENT 3: RANO RESPONSE CRITERIA**

Patients with measurable disease (bidimensional measurements) will be assessed by the RANO (radiographic assessment in neurooncology) criteria. For the purposes of this study, patients should be re-evaluated every 8 weeks with a contrast-enhanced cranial MRI scan. The response will be determined as outlined in the RANO criteria below.

**Complete Response** (requires all of the following):

- a) Complete disappearance of all enhancing measurable and non-measurable disease sustained for at least 4 weeks. In the absence of a confirming scan 4 weeks later, this scan will be considered only stable disease.
- b) No new lesions.
- c) All measurable and non-measurable lesions must be assessed using the same techniques as baseline.
- d) Patients must be on no steroids.
- e) Stable or improved non-enhancing (T2/FLAIR) lesions.
- f) Stable or improved clinically.

Note: Patients with non-measurable disease cannot have a complete response. The best response possible is stable disease.

**Partial Response** (requires all of the following):

- a) Greater than or equal to 50% decrease compared to baseline in the sum of products of perpendicular diameters (bi-dimensional measurements) of all measurable enhancing lesions sustained for at least 4 weeks. In the absence of a confirming scan 4 weeks later, this scan will be considered only stable disease.
- b) No progression of non-measurable disease.
- c) No new lesions.
- d) All measurable and nonmeasurable lesions must be assessed using the same techniques as baseline.
- e) The steroid dose at the time of the scan evaluation should be no greater than the dose at time of baseline scan.
- f) Stable or improved non-enhancing (T2/FLAIR) lesions on same or lower dose of corticosteroids compared to baseline scan.
- g) Stable or improved clinically.

Note: Patients with non-measurable disease cannot have a partial response. The best response possible is stable disease.

**Stable Disease** (requires all of the following):

- a) Does not qualify for CR, PR, or progression.
- b) The designation of stable disease requires a minimum of 4-week duration.
- c) All measurable and non-measurable sites must be assessed using the same techniques as baseline.
- d) Stable non-enhancing (T2/FLAIR) lesions on same or lower dose of corticosteroids compared to baseline scan. In the event that the corticosteroid dose has been increased, the last scan considered to show stable disease will be the scan obtained when the corticosteroid dose was equivalent to the baseline dose.
- e) Stable clinically.

**Progressive Disease** (defined by any of the following):

- a) >25% increase in sum of the products of perpendicular diameters (bi-dimensional measurements) of enhancing lesions (over baseline if no decrease) on stable or increasing doses of corticosteroids. and/or
- b) Significant increase in T2/FLAIR non-enhancing lesion on stable or increasing doses of corticosteroids compared to baseline scan or best response following initiation of therapy, not due to co-morbid events (radiation therapy, demyelination, ischemic injury, infection, seizures, postoperative changes, or other treatment effects).
- c) Any new lesion.
- d) Clear clinical deterioration not attributable to other causes apart from the tumor (e.g., seizures, medication side effects, complications of therapy, cerebrovascular events, infection, etc.). The definition of clinical deterioration is left to the discretion of the treating physician, but it is recommended that a decrease in 20% of KPS or from any baseline to 50% or less be considered, unless attributable to comorbid events.
- e) Failure to return for evaluation due to death or deteriorating condition.

**Assessment of Response** (Efficacy)

Timing of the Evaluation of Response: Assessment of response will begin with the previous MRI. All scans are to be compared to the smallest measurement scan to date.

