Stopping Rules	
For Phase 1 dose escalation, a dose level will be considered unacceptable if 2 or more patients of the 6 eligible patients experience a DLT (see below). Should all 7 patients in the Cohort be analyzable for adverse events, only the first 6 will be considered in the determination of DLTs. A patient who misses more than 7 days of PLX3397 administration during the 7-week dosing period of Cycle 1 (4 weeks) and Cycle 2 (3 weeks) for reasons other than having had a DLT will be replaced. If 2 or more patients in a Cohort experience a DLT, no patients in the Cohort will be replaced. If >2 of the first 6 patients in Dose Level -2 (400 mg/day of PLX3397) experience a protocol-defined DLT, the combination will be considered too toxic and the study will be discontinued.
 
After approximately 50% of the planned Phase 2 patients have completed their concurrent radiation therapy, an overall interim safety summary will be reviewed by the Medical Monitor and principal investigators to ensure that the potential clinical benefit outweighs the observed clinical risk to date. If the safety observations do not warrant continued enrolment, the study will be discontinued.

PK Parameters	For the Phase 1b portion of the study, a partial AUC ( $AUC_{0-6}$ ) will be calculated using samples collected from C1D8 (pre-temozolomide) and C1D15 (concurrent temozolomide). Values for $C_{max}$ and $T_{max}$ will be determined from the concentration-time profile.
PD Parameters	CD14/16 mononuclear cell counts, CSF-1, and biomarkers of kinase inhibition and myeloid cell recruitment. Surgical tissue will be evaluated for MGMT methylation, CSF-1, CSF1R, tumor-associated macrophages, and other prognostic biomarkers in order to correlate with treatment response and inform enrichment strategies for subsequent studies in this patient population. If the MGMT methylation status of the study population differs from that observed in the RTOG 0525 study, the benchmark mPFS of 5.5 months will be adjusted appropriately.
Endpoints	
Primary: Median PFS by RANO criteria
 
Secondary: Safety, OS, PK, correlative imaging
 
Exploratory: PD biomarkers

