## 10.0 DESIGN

### 10.1 Description

This will be an open label, uncontrolled Phase 1b/2 trial in patients with newly diagnosed GBM who have recovered from complete or partial surgical resection. All patients will be treated with PLX3397 in addition to standard-of-care combination radiation therapy (RT) plus temozolomide (TMZ) followed by adjuvant TMZ. During Phase 1b dose escalation, two PLX3397 administration schedules, 7 days/week vs. 5 days/week (M-F) will be explored. During Phase 2, patients will be treated with the RP2D.

There are 4 sequential periods: 1-week PLX3397 monotherapy; 6-week PLX3397/RT/TMZ combination therapy; 4-week recovery; and, PLX3397/TMZ adjuvant therapy. PLX3397 will be administered twice daily either 7 days/week or 5 days/week (Monday through Friday) starting 1 week prior to the initiation of RT and will continue twice daily either 7 days/week or 5 days/week (Monday through Friday) during the 6-week course of RT.

Phase 1b PLX3397 dose and schedule cohorts are shown in [Table 2](#).

A detailed Trial Flow Chart is available in [Section 6.0](#), and procedures by study day are provided in [Section 13.0](#).

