#### **11.1 Inclusion Criteria**

1. Male or female patients  $\geq 18$  years old.
2. Histologically confirmed definitive GBM or gliosarcoma by partial or complete surgical resection (i.e. not by biopsy only) within 5 weeks prior to PLX3397 administration (C1D1). Tumor must have a supratentorial component. For all patients, availability of an archival paraffin tumor block sufficient to generate at least 20 unstained slides; or, if a paraffin tumor block is unavailable, at least 20 unstained slides.
3. The patient must have recovered from the effects of surgery, post-operative infection, and other complications before study registration.
  - a. A diagnostic contrast-enhanced MRI or CT scan of the brain must be performed preoperatively and postoperatively prior to the initiation of radiotherapy, i.e., within 28 days (14 days preferred) prior to study drug administration (C1D1).
  - b. Patients unable to undergo MR imaging because of non-compatible devices can be enrolled, provided pre- and post-operative contrast-enhanced CT scans are obtained and are of sufficient quality.
2. Patients must receive RT at the participating institution.

3. Women of child-bearing potential must have a negative pregnancy test within 14 days of initiation of dosing and must agree to use an acceptable method of birth control while on study drug and for 3 months after the last dose. Women of non-childbearing potential may be included if they are either surgically sterile or have been postmenopausal for  $\geq 1$  year. Men of child-bearing potential must also agree to use an acceptable method of birth control while on study drug, and for 3 months after the last dose.
4. Karnofsky performance status of  $\geq 70$ .
5. Adequate hematologic, hepatic, and renal function (absolute neutrophil count  $\geq 1.5 \times 10^9/L$ , Hgb  $> 10$  g/dL, platelet count  $\geq 100 \times 10^9/L$ , AST/ALT  $\leq 2.5 \times$  ULN, creatinine  $\leq 1.5 \times$  ULN).
6. Willing and able to provide written informed consent prior to any study related procedures and to comply with all study requirements.

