#### 21.4 Efficacy Analysis

Response to treatment will be evaluated using the Response Assessment in Neuro-Oncology (RANO) criteria (Wen 2010). The response criteria are summarized in Attachment 3. All patients who are eligible for efficacy analyses will be evaluable for PFS, calculated for each subject as the number of days from the first day of treatment (C1D1) to the date of the first documented disease progression or date of death, whichever occurs first. The Kaplan-Meier method will be used to estimate the median PFS.

Statistical modeling will be used to match the experimental group to the RTOG 0525 historical group for expected prognosis based on both clinical and molecular factors, importantly the level of MGMT methylation in the tumor tissue.

For each subject with a response to therapy, duration of response will be calculated. The duration of response is defined as number of days from the date of initial response to the date of first documented disease progression or death, whichever occurs first. The Kaplan-Meier method will be used to estimate median duration of response. In the event no disease progression or death is documented prior to study termination, analysis cutoff, or the start of confounding anticancer therapy, PFS and duration of response will be censored at the date of last evaluable tumor assessments. The median duration will be compared to the historical control PFS of 5.5 months. The secondary endpoint of OS will be analyzed in a similar fashion.

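### Attachment 3 limits RANO to measurable disease and lists no progression item for growth of an existing non-measurable enhancing remnant, so the primary PFS can read too long

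*Combined protocol and SAP*

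**What the plan says.** The trial enrols "patients with newly diagnosed GBM who have recovered from complete or partial surgical resection" (Section 10.1). Section 11.1 excludes diagnosis by biopsy alone, and no criterion asks for measurable residual disease.

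The synopsis gives the primary endpoint as "Median PFS by RANO criteria". Section 21.4 says "All patients who are eligible for efficacy analyses will be evaluable for PFS", with no condition on measurability, and refers to Attachment 3 for a summary of the criteria.

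Attachment 3 begins: "Patients with measurable disease (bidimensional measurements) will be assessed by the RANO (radiographic assessment in neurooncology) criteria". It gives no separate rule for other patients. Yet two notes under complete and partial response cap patients with non-measurable disease at stable disease, so the attachment expects them to be rated. Partial response item b requires "No progression of non-measurable disease", which treats such progression as an event in its own right.

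The progression list has five items:
- a) ">25% increase in sum of the products of perpendicular diameters (bi-dimensional measurements) of enhancing lesions (over baseline if no decrease"), on a stable or rising steroid dose;
- b) a significant T2/FLAIR increase not explained by co-morbid events, including treatment effects;
- c) a new lesion;
- d) clear clinical deterioration due to tumour;
- e) non-return because of death or decline.

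Stable disease item a takes in whatever does not qualify as complete response, partial response or progression.

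**The concern.** The attachment has two faults. Its opening sentence covers fewer patients than the analysis does. Its progression list has nothing to match the non-measurable progression named under partial response.

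Partial resection can leave a thin enhancing rim or a small remnant that cannot be measured in two dimensions. If it grows while T2/FLAIR and clinical state stay stable, no progression item clearly applies and the patient is rated stable. The event is then dated at a later scan or decline, or the patient is censored at the last evaluable assessment.

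Either way the recorded PFS is longer than it should be. In a single-arm comparison with a historical median, that favours PLX3397, and no concurrent arm shares the error. Sites could also resolve the gap differently.

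**Working it through.** **The text, item by item.** Take an existing non-measurable enhancing remnant that grows on MRI, with stable T2/FLAIR, no new focus and a stable clinical state.

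- Item a needs products of perpendicular diameters. The attachment equates bidimensional measurement with measurable disease, so the remnant has no baseline product to increase by 25%. The attachment does not say what happens when it grows to measurable size.
- Items b, d and e are not met, by construction.
- Item c is not met, because the lesion already existed.
- Stable disease: item a is met by default, and T2/FLAIR and clinical state are stable. The rating is stable disease.

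After a complete resection there is no remnant, so fresh enhancement falls under item c. The gap is therefore confined to existing non-measurable enhancing residual disease.

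**Illustrative size.** The documents give neither the share of such patients nor the delay.

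Inputs from the documents: benchmark median 5.5 months and 22 events in about 31 patients at one-sided 0.1 (Section 21.2); target median about 8 months (Section 10.5); scans about every 8 weeks (Section 13.12).

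Assumptions: PFS is exponential with true median 5.5 months, and a share f of patients has every event recorded D months late.

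- λ = ln 2 / 5.5 = 0.1260 per month; D = 56 / 30.4375 = 1.84 months; exp(λD) = 1.261.
- For t ≥ D, S(t) = (1 − f)·exp(−λt) + f·exp(−λ(t − D)).
- Setting S = 0.5: observed median = 5.5 + (1/λ)·ln(1 − f + f·exp(λD)).

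The last column comes from 40,000 simulated trials of 31 patients analysed at the 22nd event, using a one-sample test calibrated to 0.10 under the exponential null. The form of the test is also an assumption.

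| f | 1 − f + f·exp(λD) | Observed median (months) | False-positive rate |
|---|---|---|---|
| 0 | 1.000 | 5.5 | 0.10 |
| 10% | 1.026 | 5.7 | 0.13 |
| 20% | 1.052 | 5.9 | 0.16 |
| 30% | 1.078 | 6.1 | 0.19 |
| 50% | 1.130 | 6.5 | 0.27 |

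The row f = 0 returns the plan's own 5.5 months and 0.1 level. The shift is 0.2 to 1.0 months, against a planned gain of 8 − 5.5 = 2.5 months.

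**Why this is an upper bound for the share and delay assumed.** The model delays every event in the subgroup, including deaths, clinical declines, new lesions and T2/FLAIR progression, none of which the gap delays. If 20% of patients have such a remnant and a quarter to a half of their events are delayed, the effective share is 5 to 10% and the median is about 5.6 to 5.7 months.

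**Longer interval.** From 01 October 2017 scans are about 12 weeks apart (Section 13.10). With D = 84 / 30.4375 = 2.76 months, the formula gives 5.8 to 7.0 months for f = 10 to 50%. This could apply only to assessments after that date, so it is not part of the main range.

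**The case against.** Four objections have weight.

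- **Attachment 3 is a summary.** Section 21.4 says response will be evaluated by the cited RANO publication. If that publication carries the missing item, a site that knows it may apply it. This cannot be checked here. Attachment 3 itself says response is determined by the criteria it lists, so the text sites are given should be complete.
- **Item a refers to enhancing lesions, while partial response item a refers to measurable enhancing lesions.** With no size threshold stated, a site could count a remnant once it has two diameters. That reading is possible, but it leaves the missing baseline product unresolved and lets sites differ.
- **The opening sentence may be loose drafting.** The notes, and the requirement to assess measurable and non-measurable sites alike, show that these patients were meant to be rated. That stands, and it supports correcting the sentence.
- **The benchmark may carry the same effect.** The documents do not say which progression rule lies behind 5.5 months. The planned matching on clinical and molecular factors (Section 21.4) and the adjustment for MGMT status (synopsis) do not address how progression was assessed.

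A reader might go further and infer that every resected patient, or every complete resection, escapes a progression call, or that patients without measurable disease drop out of PFS. The documents do not support this. Recurrence after complete resection is a new lesion, three other triggers remain, and Section 21.4 keeps all efficacy patients in the analysis. The notes cap best response at stable disease; they do not tell sites to call a growing remnant stable.

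**Conclusion.** The inconsistency and the missing item are both in the text, and they affect the rule that dates the primary endpoint. The direction is clear for patients with a small or rim-like enhancing remnant: a late call lengthens PFS. The effect on the comparison also depends on the rule behind the benchmark.

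The size is not established. About 5.7 to 6.5 months in place of 5.5 is an upper bound that rests on exponential PFS, an assumed share of 10 to 50%, and every event in that share being one 8-week scan late. The real effect is smaller if only some events are delayed. A reader might infer that the gap could account for most of the planned gain to about 8 months. That would need longer delays in a large share of patients, with deaths and clinical declines delayed as well, and nothing in the documents supports it.

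This should be corrected before the analysis. It does not by itself invalidate the endpoint.

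**What to change.** Amend Attachment 3 and the analysis text as follows.

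1. State that the progression criteria apply to every patient in the efficacy population, measurable or not.
2. Add to the progression list: *clear progression of existing non-measurable enhancing disease, including growth to measurable size, compared with the reference scan, not due to treatment effects or other co-morbid events.*
3. Keep the measurable-disease restriction for complete and partial response and for duration of response only.
4. Record measurable disease, yes or no, on the baseline scan taken 3 to 4 weeks after radiotherapy, and report PFS by that status as a sensitivity check.
5. Confirm that the rule matches the one behind the 5.5-month benchmark, or state the difference as a limitation.

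Cost: a short amendment and one CRF field, using the same scans. Some progression calls will come earlier and involve some reader discretion in an open-label trial, and the median PFS may be slightly less favourable. Patients with such a remnant who have already been rated will need a second look at their scans. Progression also bears on how long treatment continues (Section 13.12). The change is proposed for dating the endpoint, and the sponsor and investigators should settle its bearing on treatment.

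### The notes to complete and partial response in Attachment 3 lack the word *only* and so contradict the response items for patients who have both measurable and non-measurable disease

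*Combined protocol and SAP*

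**What the plan says.** Section 21.4 evaluates response by the RANO criteria, cites the published source, and adds that "The response criteria are summarized in Attachment 3". Attachment 3 begins: "Patients with measurable disease (bidimensional measurements) will be assessed by the RANO" criteria.

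The items for the two response categories mention non-measurable disease four times:

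- CR item a: "Complete disappearance of all enhancing measurable and non-measurable disease sustained for at least 4 weeks".
- CR item c: "All measurable and non-measurable lesions must be assessed using the same techniques as baseline". PR item d repeats this requirement.
- PR item b: "No progression of non-measurable disease".

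A note then follows each list. Under CR: "Patients with non-measurable disease cannot have a complete response. The best response possible is stable disease". Under PR: "Patients with non-measurable disease cannot have a partial response. The best response possible is stable disease".

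Responder status is used in Section 21.4: "For each subject with a response to therapy, duration of response will be calculated", with a Kaplan-Meier median.

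**The concern.** The notes and the items disagree about a patient who has at least one measurable enhancing lesion and also some non-measurable disease. The items describe how such a patient can respond. The notes, which carry no qualifier, say that a patient with non-measurable disease cannot. I found no definition of measurable or non-measurable disease in the protocol, no sentence limiting the notes, and no rule on which text prevails.

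At stake is who counts as a responder. An assessor who follows the notes would record stable disease where one who follows the items would record CR or PR, and both could cite Attachment 3. The study runs at about 7 to 10 sites (Section 10.3), and I found no provision for a central imaging read that would impose one interpretation. Patients scored as stable drop out of the duration-of-response set.

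**Working it through.** No arithmetic applies, and the plan gives no figure to reproduce. The check is to apply the items and the notes to each possible baseline pattern.

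| Baseline disease | CR and PR items | Notes, read literally | Agree? |
|---|---|---|---|
| Measurable only | CR or PR possible | Not triggered | Yes |
| Non-measurable only | PR not possible: item a needs a decrease in measurable lesions. CR not expressly barred | Stable disease at best | Compatible: the note adds the bar on CR |
| Both | CR or PR possible | Stable disease at best | **No** |

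**What the literal reading does to the items.** It leaves response open only to the first row. Those patients have no non-measurable disease at baseline, so the references to it in CR items a and c and PR item d, and the whole of PR item b, would have nothing at baseline to act on. That is a sign that the notes were meant for the second row.

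**Whether the opening sentence settles it.** It speaks of patients with measurable disease, and the notes speak of patients with non-measurable disease. If these are two separate classes, a patient with both belongs to the first and the notes do not apply. But the sentence does not say that the classes are exclusive. Read strictly, it places patients without measurable disease outside the criteria altogether, which would leave the notes applying only to patients with both kinds. It points to the intended meaning without fixing it.

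**Where responder status is used.**

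- Duration of response (Section 21.4): calculated in responders only, so affected.
- Exploratory correlations with clinical response (Section 21.7.2, and PD Parameters in the Synopsis): may be affected. Section 21.7.2 plans no formal test of PD endpoints.
- PFS: not affected. The progressive disease items in Attachment 3 do not invoke the notes. The 22 events, about 31 patients and 80% power in Section 21.2 therefore stand.
- The Endpoints row of the Synopsis lists neither response rate nor duration of response.

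**The case against.** The best defence is that the intended meaning can be recovered. A reading that gives every item work to do is preferable to one that empties several of them, and the opening sentence supports it. Section 21.4 also names the published criteria as the standard and calls Attachment 3 a summary, so assessors have another source. Much of this stands: the defect is a contradiction with a likely intended resolution, and disagreement between assessors is a possibility, not something the documents show. But the resolution is not written down, and whether the published criteria supply it cannot be checked from the documents.

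Three stronger readings are tempting and are not supported:

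- *A patient with both kinds of disease can never be a responder.* This holds only if the notes override the items, and nothing says that they do.
- *A stated share of responders is lost.* Suppose 30 patients with measurable disease and 20% true response: 30 × 0.20 = 6 responders. If 20%, 40% or 60% of them also have non-measurable disease, the literal notes leave 6 × 0.8 = 4.8, 6 × 0.6 = 3.6 or 6 × 0.4 = 2.4. Every input is assumed, and so is independence of response from disease pattern. The loss of 20% to 60% merely returns the assumed share. The documents do not describe residual disease after resection.
- *The biomarker analyses in Section 21.4 are diluted.* The sentence there on treatment response closes a paragraph on tumour-growth modelling and may mean Days Gained and Radial Treatment Response, which the notes do not touch.

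**Conclusion.** Wrong as written, with limited reach. Attachment 3 contradicts itself for patients with both kinds of disease: CR items a and c and PR items b and d provide for their response, and both notes, taken literally, deny it. Applying the notes as worded would record such responders as stable.

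The consequence is confined to the duration-of-response estimate and exploratory correlations with clinical response. The primary analysis and its sample size are untouched. The number of patients affected cannot be computed, because the documents do not give the share with both kinds of disease. The conclusion rests on the wording of Attachment 3 alone and on no numerical assumption.

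**What to change.** In both notes, insert *only (no measurable enhancing lesion at baseline)* directly after the words *non-measurable disease*. The notes then agree with the CR and PR items.

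The sponsor should also confirm which scan is the response baseline. The Synopsis (Study Procedures) names the scan about 3 to 4 weeks after radiotherapy as baseline for determining progression, while the Assessment of Response paragraph in Attachment 3 starts response assessment from the previous MRI. These do not settle the point, and the wording change does not depend on which scan is chosen.

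The cost is a few words in two notes and one confirmation. It needs no new data or assessments and leaves the sample size unchanged.
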